4 STUDY DESIGN

4.1 OVERALL DESIGN

This is a prospective, open-label, study during which 60 subjects with FI will be treated with the Minnesota Medical Technologies Anal Insert Device. Up to 150 subjects may be enrolled to ensure 60 subjects are eligible to participate in the Treatment Period. This study will consist of a baseline period and a treatment period. A fitting period, prior to the treatment period, will determine which of two devices sizes each study subject will use during the treatment period. Up to [REDACTED] of these 60 subjects will participate in a [REDACTED] sub-study to evaluate the effects of the Minnesota Medical Technologies Anal Insert Device on [REDACTED].

Subjects will sign the informed consent form at the screening visit. After signing the consent form, the subjects are considered enrolled in the study. At this visit, medical history and concomitant medications will be collected, as well as vital signs, and the ability of the subject to retain the device will be evaluated to determine eligibility for the study. Eligible subjects will proceed to baseline period (baseline bowel diary), during which subjects will record all bowel movements in a daily diary and complete questionnaires for 4 weeks. Subjects will be provided with a [REDACTED] and a [REDACTED] for use at home during the baseline period. Subjects will deliver, or send the [REDACTED] to the study site. Subjects who have 4 or more FI episodes during this 4-week baseline period will be eligible to continue to the fitting and treatment periods.

Subjects will return to the Mayo Clinic Rochester study site to have diaries assessed for compliance and eligibility for treatment and, if eligible, will complete quality of life questionnaire. Subjects eligible for treatment will be trained on the insertion and evacuation of the device and will be provided with instructions on how to contact [REDACTED] to have the devices shipped to them.

During this visit to the Mayo Clinic study site, subjects will receive the following assessments: baseline anoscopy (if not already performed within 6 months of informed consent), assessment of [REDACTED], a [REDACTED], and [REDACTED]. In up to [REDACTED] subjects who agree to participate in the [REDACTED] sub-study, [REDACTED] will be assessed [REDACTED].

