6.1.2 DEVICE ADMINISTRATION

The sizes to be evaluated in this study are:

- Minnesota Medical Technologies Anal Insert Device 10 mm size – to be inserted in the anorectum during the day. Subjects who have nocturnal FI should also use the device at night.
- Minnesota Medical Technologies Anal Insert Device 13 mm size – to be inserted in the anorectum during the day. Subjects who have nocturnal FI should also use the device at night.

At the screening visit, the 10 mm, and, if necessary thereafter, the 13 mm device will be inserted into the rectum to determine if the device stays in situ while subjects are ambulating. Subjects who can retain neither device size will be withdrawn from the study.

Study subjects eligible for the study at the end of the baseline period will be given instructions as to ordering the study devices to be shipped to them by Minnesota Medical Technologies. The clinical site will train study subjects in the proper use of devices.

Eligible study subjects will proceed to a up to 4-week fitting period where subjects will evaluate which of two device sizes (10mm or 13mm) is preferred. Subjects who can retain the 10mm device at the screening visit will begin the fitting period with the 10mm device. Subjects who cannot retain the 10 mm but can retain the 13 mm device will begin the fitting period with the 13 mm device. The sequence of events for the fitting period will be as follows:

- 1) Subjects who begin with the 10 mm device will use the device for a minimum of 2 weeks during the fitting period. , Subjects will be asked to complete daily bowel diaries to determine the percent reduction in FI episodes, and subject comfort will be assessed using question #7 on the QUEST questionnaire. If greater than or equal to 75% reduction in FI episodes is observed during this fitting period, the subject will proceed immediately to the treatment period and will continue using the 10mm device for the entire treatment period. If the reduction in FI episodes is less than 75%, and the QUEST score is 1-2 (indicating dissatisfaction with comfort), the subject will proceed immediately to the treatment period and will continue using the 10mm device for the entire treatment period. If the reduction in FI episodes is less than 75%, and the QUEST score is 3-5 (indicating satisfaction with comfort), the participant will use 13 mm devices

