for a minimum of 2 weeks as their fitting period and complete daily bowel diaries. At the end of this fitting period, the subject comfort will be reassessed with question #7 of the QUEST questionnaire. Subjects who report QUEST scores of 1-2 (indicating dissatisfaction with comfort) with the 13mm device will use the 10mm device for the entire treatment period. However, subjects who report QUEST scores of 3-5 (indicating satisfaction with comfort) at the end of the fitting period will proceed immediately to the treatment period and will continue using the size 13mm device for the entire treatment period.

- 2) Subjects who begin with the 13mm device will use the device for a minimum of two weeks during the fitting period. Thereafter, the subject will proceed to the treatment period and will continue using the 13mm device for the entire treatment period.

Subjects will be contacted at least twice per month during the fitting period. Attempts will be made to space these calls at an interval of 7 days. The devices which they are assigned to receive will be dispensed to study subjects by Minnesota Medical Technologies for use during the treatment period.

The devices will be packaged individually. Each subject will self-administer the devices. Subjects will be provided instructions for how to order the device and also an Instructions For Use, both of which will have Institutional Review Board (IRB) approval prior to use.

After the treatment period, all individuals who withdraw for reasons other than personal preference (i.e., for medical reasons) and a minimum of 50% of all patients shall undergo an evaluation by anoscopy following the treatment period to assess for device related trauma

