6.3 MEASURES TO MINIMIZE BIAS: RANDOMIZATION AND BLINDING

This is a within-subject control study with a 4-week baseline period followed by a 2 to 4-week fitting period and a 4-week treatment period. Up to [REDACTED] subjects who meet all inclusion and meet no exclusion criteria at the end of the baseline phase of the study may be included in the optional [REDACTED] sub-study

Subjects who are candidates for screening into the study will be evaluated for eligibility by the Investigator to ensure that the inclusion and exclusion criteria have been satisfied. Once the subject signs the informed consent, they are considered enrolled in the study. At that time, the study site personnel will register the subject and assign a sequential and unique subject number. Once a subject number has been assigned, it cannot be reused.

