Subjects will complete a Quebec User Evaluation of Satisfaction with assistive Technology (QUEST) questionnaire to assess their level of satisfaction with the study device. The questionnaire gathers information relating to user satisfaction with various aspects of the device and service provided during treatment.

Exploratory Study Assessments: [REDACTED] Procedures (for [REDACTED] sub-study subjects only)

A schema and rationale for the [REDACTED] is as follows.

Table 1. Schedule of Events – [REDACTED].

Steps	Purpose
i) [REDACTED] will be performed if this not been performed previously*	i) Evaluate for [REDACTED]
- ii) [REDACTED] and randomize subjects, equally [REDACTED] to one	ii) Evaluate device [REDACTED]

of [REDACTED] groups: [REDACTED] Minnesota Medical Technologies Anal Insert Device (10 mm), and Minnesota Medical Technologies Anal Insert Device (13 mm). [REDACTED]. Measure [REDACTED]. Remove subjects [REDACTED]. Then [REDACTED]. Ask subjects and measure [REDACTED]. Compare [REDACTED].
 
iii) Add [REDACTED] (until [REDACTED]) to [REDACTED].
 
iv) [REDACTED] subject [REDACTED] randomize subjects to 10 mm or 13 mm device. Obtain [REDACTED]
	
iii) Determine [REDACTED]
 
iv) Assess a) relationship between [REDACTED] b) rectoanal [REDACTED] and c) ability to [REDACTED].

--	---

*With one exception, ie, the use of the Minnesota Medical Technologies Anal Insert Device, [REDACTED] is comparable to that performed in clinical practice.

** [REDACTED]: The [REDACTED] consists of the [REDACTED] the Minnesota Medical Technologies Anal Insert Device [REDACTED]. The [REDACTED] prepared by [REDACTED] the device. A [REDACTED], approximately [REDACTED], is passed through [REDACTED]. The [REDACTED] is placed [REDACTED] and [REDACTED] with the [REDACTED].

Randomization to 10 or 13 mm device

This [REDACTED] include these assessments arranged in chronological order. We anticipate that these studies will be performed in [REDACTED]. Established techniques used in our clinical practice and research will be used [REDACTED]

[REDACTED]

After [REDACTED], the anal [REDACTED]

[REDACTED] in conjunction with a [REDACTED]

[REDACTED] will be categorized [REDACTED]

[REDACTED]).

(ii) [REDACTED] test

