8.2 SAMPLE SIZE DETERMINATION

The sample size determination was based on literature review. In a controlled clinical trial with clonidine, the mean and standard deviation (SD) for weekly FI episodes over a 4 week baseline period was 2.642 and 1.066 respectively in the placebo group.²⁹

Assuming a mean frequency of 2.6 and a very conservative estimated SD of differences (post-pre treatment) of 1.3, a sample size of 13 subjects provides 90% power with a two sided paired t test and an alpha level of 0.05 to detect a 50% reduction (i.e., from 2.6 to 1.3 episodes/week) in the number of episodes of FI. Hence, a sample size of 30 FI subjects per group (i.e., 10mm and separately 13 mm inserts) is more than sufficient.

In order to test whether the treatment provides an improvement up to 60% response rate (50% response) from an assumed historical rate of 30%, the exact one-sample binomial test (2-sided) will be used at the 0.05 level. A sample size of n=30 provides 90% power to detect this effect.

No previous studies have evaluated [REDACTED]. We estimated that FI subjects [REDACTED] will [REDACTED] of the [REDACTED] (i.e., [REDACTED]). If [REDACTED] with a sample size of [REDACTED] in the [REDACTED] and [REDACTED] in the [REDACTED] (i.e., [REDACTED] devices), provides [REDACTED] [REDACTED].

For anoscopy, the sample size of 31 patients (i.e., 52%), provides 80% power to detect an event rate of 5% and 96% power to detect an event rate of 10%. In this context, an event refers to a side effect such as an anal fissure.

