8.4.2 ANALYSIS OF THE PRIMARY AND SECONDARY EFFICACY ENDPOINT(S)

[REDACTED]
detailed methods for the analyses outlined below,

All bowel diary parameters (e.g., stool frequency, form, urgency, use of rescue medications, and FI) will be averaged first for each day and then over 4 weeks (baseline period and the last 4 of 12 weeks (approximately Weeks 9-12, treatment period) in each subject. These responses will also be assessed using ANCOVA models, with the corresponding baseline value as the primary covariate. [During the fitting period (approximately weeks 5-8), bowel diaries and questionnaires will be maintained to determine the right size of device. However, these data will not be used to evaluate the efficacy of the device.]

The analyses of the primary and secondary quantitative endpoints will utilize analysis of covariance (ANCOVA) models using corresponding baseline measurements, if available, as covariates. The adequate relief endpoint will first be summed over 4 treatment weeks, and then assessed using the Wilcoxon rank sum test. Treatment effects between groups (i.e., 10 mm vs 13 mm) will be evaluated, as appropriate with ANCOVA adjusted for the baseline variable. Individual adverse events (AEs) will be summarized and, where appropriate, (i.e., for parameters that are recorded during baseline and treatment bowel diaries such as pain during defecation), the overall frequency of AEs be compared using the Wilcoxon rank sum test. For the volume of FI episodes, a weighted score will be computed as follows (proportion of minor episodes*2 + proportion of major episodes*3).²⁵ An FI episode is defined as any episode of stool leakage that is more than a stain. A “minor FI episode” is more than a stain but not an entire bowel movement. A “major FI episode” is an entire bowel movement.

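### The 10 mm vs 13 mm ANCOVA in section 8.4.2 compares groups that the main study forms partly on early response and comfort, and baseline adjustment cannot correct for that

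*Combined protocol and SAP*

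**What the plan says.** **The comparison.** Section 8.4.2 plans a between-size analysis: "Treatment effects between groups (i.e., 10 mm vs 13 mm) will be evaluated, as appropriate with ANCOVA adjusted for the baseline variable". The visible text names no covariate other than baseline and does not say when the comparison would be inappropriate.

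**The design.** Section 6.3 describes the main study this way: "This is a within-subject control study with a 4-week baseline period followed by a 2 to 4-week fitting period". Allocation of size by chance appears only in the sub-study procedures of section 7.1, under "Randomization to 10 or 13 mm device". Section 8.3, however, defines the intent-to-treat set for both the main study and the sub-study in terms of randomised subjects.

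**How size is set.** Section 6.1.2 starts subjects who retain the 10 mm device at screening on 10 mm, and those who retain only the 13 mm on 13 mm. For those starting on 10 mm, early response comes first: "If greater than or equal to 75% reduction in FI episodes is observed during this fitting period, the subject will proceed immediately", and they stay on 10 mm. Below that cut-off, QUEST item 7 decides whether 13 mm is tried. Those then dissatisfied "with the 13mm device will use the 10mm device for the entire treatment period".

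**Numbers.** Section 4.1 fixes only the total, a "study during which 60 subjects with FI will be treated". Section 8.2 nonetheless concludes that "a sample size of 30 FI subjects per group (i.e., 10mm and separately 13 mm inserts) is more than sufficient", and for the responder test that "A sample size of n=30 provides 90% power to detect this effect", without saying whether that n is per size.

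**The concern.** A between-group ANCOVA estimates a treatment effect only if, given the covariates, group membership is unrelated to how a subject would respond. Here membership is decided partly by how the subject did respond, two or more weeks earlier, on the same diary outcome. Comfort, which may go with response, also decides it. Both arise after baseline, so neither the ANCOVA covariate nor the baseline comparison in section 8.4.5 deals with them.

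A p-value or adjusted difference between sizes could then be reported as one size working better, when it reflects who was routed to which size. The reference to randomised subjects in 8.3 and the even split implied in 8.2 make that reading easier.

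**Working it through.** **1. Routing rule (section 6.1.2), laid out.**

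| Retains 10 mm at screening | FI reduction on 10 mm in fitting | QUEST 7 on 10 mm | QUEST 7 on 13 mm | Final size |
|---|---|---|---|---|
| No (retains 13 mm) | not used | not used | not used | 13 mm |
| Yes | ≥75% | not used | not used | 10 mm |
| Yes | <75% | 1-2 | not used | 10 mm |
| Yes | <75% | 3-5 | 1-2 | 10 mm |
| Yes | <75% | 3-5 | 3-5 | 13 mm |

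Every early good responder who started on 10 mm stays there. The 13 mm group holds the non-retainers and the comfortable subjects with less early response. The 10 mm group also keeps poor early responders who disliked a device. No row contains both sizes, so adding these variables as covariates would rest on extrapolation rather than on comparable subjects.

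**2. Why baseline adjustment fails.** Let B be baseline frequency, R a subject's underlying responsiveness, F the fitting count and Y the treatment-period count. F and Y both depend on B and R, and size S depends on F. Given B, S still carries information on R. So E(Y | B, S=13) - E(Y | B, S=10) is in general not zero, even when the two sizes work equally well.

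**3. Illustration with equal true effects.** The following are assumptions, not properties of the trial:
- 60 subjects; 4-week baseline count gamma-Poisson with mean 4 × 2.6 = 10.4 and SD 4 × 1.066 = 4.26 (section 8.2), kept if at least 4;
- individual reduction logit-normal, centred at 50%, logit SD 1.0;
- 2-week Poisson fitting count, then the table above;
- 5% cannot retain 10 mm; 60% are comfortable on 10 mm and 85% on 13 mm.

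Baseline-adjusted coefficient, 13 mm minus 10 mm (positive means more episodes on 13 mm):

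| Comfort-response correlation | Spurious difference, episodes/week |
|---|---|
| 0 | about +0.27 |
| 0.5 | about -0.04 |
| 0.8 | about -0.19 |

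At correlation 0 the nominal 5% test rejected in about 22% of trials. Recentring so that 70% of subjects have at least a 50% reduction (the expectation in section 8.4.1) gives +0.29, +0.01 and -0.15. At correlation 0.5 the sign also turns on how 13 mm comfort is modelled: -0.04 if it is tied to response, +0.03 to +0.04 if it is independent of response or identical to 10 mm comfort. For scale, the planned effect is 2.6 - 1.3 = 1.3 episodes/week, and 0.27/1.3 = 21% of it.

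**4. The figures in section 8.2.** Paired t, two-sided 0.05, standardised effect 1.3/1.3 = 1, noncentrality √n. Power is 88.3% at n=12 and 91.1% at n=13, so the plan's 13 reproduces. It is 98.9% at 20 and above 99.9% at 30.

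Exact binomial, 30% vs 60%: reject at the smallest r with P(X ≥ r | 0.30) ≤ 0.025.

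| n | r | Power at 60% |
|---|---|---|
| 15 | 9 | 61.0% |
| 20 | 11 | 75.5% |
| 25 | 13 | 84.6% |
| 30 | 15 | 90.3% |
| 60 | 26 | 99.7% |

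The plan's 90% at n=30 also reproduces. The arithmetic is sound. What has no calculation or rule behind it is the 30/30 split.

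**The case against.** **Redaction and conditional wording.** Section 8.4.2 opens with redacted text that seems to point to more detailed methods. It also calls baseline the main covariate rather than the sole one, and makes the comparison conditional. This stands as a limit on confidence: if the hidden text already restricts the contrast or labels it exploratory, only the wording in 8.2 and 8.3 remains. It does not answer the point on the visible text, which gives no rule that would prevent the bias.

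**No size claim in the objectives.** Outside redacted exploratory items, section 3 lists no 10 mm vs 13 mm objective, and section 8.1 assesses each size against baseline. This is fair, and it keeps the point away from the primary result. The between-size analysis is still planned.

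**Transparency.** The routing rule is set out in full in several places, and 8.4.2 says openly that fitting diaries choose the size and are not used for efficacy. A reader might infer a contradiction there; there is none.

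**Sample size.** A reader might infer that 8.2 is underpowered. The documents do not support that. The sentence on 30 per group follows from the paired t, which keeps at least 90% power in any size group of 13 or more, so down to a 47:13 split. The binomial n=30 is not stated to be per size.

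**Conclusion.** The concern holds for the main-study 10 mm vs 13 mm contrast and should be fixed, with moderate confidence given the redaction. Following the visible text produces a comparison selected partly on an early reading of the outcome, and the named adjustment cannot repair it.

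Three stronger readings are not supported:
- **That the bias works against 13 mm.** It does if comfort and retention are unrelated to response. It can vanish or reverse if uncomfortable subjects also respond worse, or if subjects who cannot retain 10 mm respond better. The documents settle neither, and the range of roughly +0.3 to -0.2 episodes/week shows only that the distortion can be material.
- **That the primary result is compromised.** The pooled within-subject comparison with baseline does not depend on the size contrast.
- **That the size-versus-baseline assessments in 8.1 should be demoted.** They are within-subject and nothing here argues against them.

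The power loss in a single size (75.5% at 20, 61.0% at 15) applies only if the binomial claim is read per size and the true response rate is 60%.

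**What to change.** - **8.4.2:** drop the main-study 10 mm vs 13 mm ANCOVA. Otherwise label it exploratory and non-randomised, and state that size was assigned partly by fitting-period response and comfort.
- **8.3:** limit 'randomized' to the sub-study and define the main-study analysis set without it.
- **8.2:** say that numbers per size are not fixed. The paired-t claim holds for any size group of 13 or more. The binomial claim applies to the pooled 60, and to one size only if about 30 subjects end up on it.
- **8.1:** keep each size versus baseline, reported with its actual n and 95% CI. For an observed 60% response the exact interval would be 41-77% at n=30, 36-81% at n=20 and 32-84% at n=15.

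The cost is a few sentences, with no extra subjects, visits or data. The main study loses a confirmatory size comparison, which this allocation cannot support; the sub-study's randomised comparison is untouched. The fitting rule itself is not at issue.

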8.3 POPULATIONS FOR ANALYSES

Male and female, aged 18 and above, with a diagnosis of fecal incontinence. For the main and the sub-study, the analyses will follow the intent to treat (ITT) paradigm with all subjects randomized included in the analyses. Subjects with missing values for a particular endpoint will have their missing values imputed using the corresponding overall mean value from all subjects with non-missing data for that endpoint. An adjustment in the ANCOVA error degrees of freedom (subtracting one for each imputed value) will be made to account for the imputation. A similar adjustment for the Wilcoxon rank sum test (adjusting the degrees of freedom for the t-approximation) will also be examined. Similar analyses will be performed for the completer cohorts, i.e., all subjects who completed the 4 week treatment bowel diary and the [REDACTED] sub-study. For the bowel diary study, the modified ITT (mITT) cohort, which comprises those subjects who entered treatment and completed at least 1 week of device use will also be considered.

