8.4.5 BASELINE DESCRIPTIVE STATISTICS

The intervention groups will be compared on baseline characteristics, including demographics and clinical features using descriptive statistics.

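### The 10 mm versus 13 mm contrasts in 8.4.2 compare groups selected partly on response and comfort, and the visible text does not say what the diary adverse-event rank-sum test compares

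*Combined protocol and SAP*

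**What the plan says.** **Size contrast.** Section 8.4.2 states: "Treatment effects between groups (i.e., 10 mm vs 13 mm) will be evaluated, as appropriate with ANCOVA adjusted for the baseline variable". It also says that fitting-period diaries serve to find the right size, and adds: "However, these data will not be used to evaluate the efficacy of the device".

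**How size is decided.** Section 6.1.2 (also 1.1 and 1.2) sets it by rule:
- A subject who cannot retain 10 mm at screening but retains 13 mm starts on 13 mm and stays there.
- A subject starting on 10 mm whose fitting-period reduction reaches 75% stays on 10 mm.
- "If the reduction in FI episodes is less than 75%, and the QUEST score is 3-5 (indicating satisfaction with comfort"), the subject tries 13 mm. With a reduction below 75% and a score of 1-2, the subject stays on 10 mm.
- After trying 13 mm: "Subjects who report QUEST scores of 1-2 (indicating dissatisfaction with comfort) with the 13mm device will use the 10mm device". The others keep 13 mm.

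**Diary adverse events.** For items recorded "during baseline and treatment bowel diaries such as pain during defecation), the overall frequency of AEs be compared using the Wilcoxon rank sum test", 8.4.2 does not say what is set against what. Section 6.3 says: "This is a within-subject control study with a 4-week baseline period". Section 8.4.5 speaks of groups: "The intervention groups will be compared on baseline characteristics". Section 8.4.4 promises summary statistics for safety and does not settle the matter. For imputed values, 8.3 provides: "A similar adjustment for the Wilcoxon rank sum test (adjusting the degrees of freedom for the t-approximation) will also be examined".

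The start of 8.4.2 is blacked out next to a mention of detailed methods, so fuller methods may exist elsewhere.

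**The concern.** Fitting-period response predicts treatment-period response, because both come from the same subject using the device. A rule that moves comfortable subjects with less than 75% reduction to 13 mm therefore puts more of the weaker responders there before the outcome is measured. Baseline FI frequency says little about how a subject responds to the device, so adjusting for it cannot undo this. A reader of the ANCOVA could conclude that 13 mm works less well when the sizes do not differ.

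The diary adverse-event test has a different weakness under each reading. As baseline versus treatment, a two-sample test is applied to two measurements on the same people. As 10 mm versus 13 mm, the test suits independent groups, but comfort helped form those groups and comfort is close to the pain item being tested. With the comparator unnamed, the choice could also be made after the data are seen.

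**Working it through.** **1. The plan's own figure.** Section 8.2 uses a paired t test with difference 1.3 and SD of differences 1.3, so d = 1.3/1.3 = 1.0. Noncentral-t power at two-sided 0.05 is 88.3% for n = 12 and 91.1% for n = 13. The stated 13 subjects for 90% power reproduces, and the plan itself treats before and after as paired.

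If the SD is 1.066 in both periods, these figures imply a within-subject correlation for FI episodes of 1 − 1.3²/(2 × 1.066²) = 1 − 1.69/2.273 = 0.26. No correlation is given for adverse-event items.

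**2. Size ANCOVA with equal true effects.** From the documents: 60 subjects, the 75% rule, a baseline of at least 4 episodes, and a 4-week mean of 4 × 2.6 = 10.4 with SD 4 × 1.066 = 4.26. Assumed: gamma-Poisson counts; a true reduction per subject with mean 60% and SD 0.16 or 0.24 (beta); a two-week fitting count at the same rate; 10% starting on 13 mm. Percent reduction is regressed on size and baseline. The switching share is the proportion of subjects below 75% who end on 13 mm.

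| Switching share | False rejection, SD 0.16 | False rejection, SD 0.24 |
|---|---|---|
| 30% | 10% | 16% to 19% |
| 60% | 19% | 41% |
| 80% | 31% | 65% |

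At 30% and 60% switching, 13 mm appears worse by 6 and 9 percentage points (SD 0.16) or 11 and 17 points (SD 0.24). At 80% and SD 0.24 the figure is 22 points.

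Baseline adjustment removes little. At 30% switching the bias falls from 6.6 to 5.8 points (0.8/6.6 = 12%) for SD 0.16, and from 11.5 to 10.9 (0.6/11.5 = 5%) for SD 0.24. If all subjects respond alike, false rejection is only 6% to 7%, so the bias comes from real differences in response between subjects.

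A second model, with lognormal residual rates and treatment-period frequency as outcome, gave 30% to 61% false rejection when 60% to 80% of subjects were comfortable. There 13 mm appeared worse by 0.37 to 0.71 episodes per week. The direction is the same.

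**3. Diary adverse events as baseline versus treatment, n = 60 pairs.** The rank-sum test takes the variance of the difference as about 2σ²/n; with within-subject correlation ρ it is about 2σ²(1 − ρ)/n. The null statistic then has SD near √(1 − ρ), and the true size is about 2Φ(−1.96/√(1 − ρ)). For ρ = 0.5 this is 2Φ(−2.77) = 0.6%. Simulation, with each pair of powers given as rank-sum / signed-rank:

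| Item (assumed) | ρ | Rank-sum size | Power |
|---|---|---|---|
| Normal, 0.35 SD worse | 0.3 | 2.1% | 45% / 59% |
| | 0.5 | 0.6% | 45% / 75% |
| | 0.7 | 0.05% | 43% / 92% |
| Common count, mean 3 to 5 of 28 days, 52% zeros | 0.3 | 2.3% | 63% / 62% |
| | 0.5 | 0.9% | 65% / 73% |
| | 0.7 | 0.2% | 67% / 89% |
| Rare count, mean 1 to 2.5 days, 84% zeros | 0.3 | 3.3% | 74% / 66% |
| | 0.5 | 2.1% | 76% / 75% |
| | 0.7 | 0.8% | 78% / 87% |

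For a still sparser item (95% zeros at baseline, mean 0.3 to 1.2 days), power is 70% / 61%, 72% / 67% and 72% / 76% at the three correlations. Size is below 5% in every cell of the table. Power is lost for continuous items from 0.3 and for common counts from about 0.5. For rare items it is not clearly lost until about 0.7.

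**4. Diary adverse events as 10 mm versus 13 mm.** Assumed: the same true pain on both sizes (mean 5 of 28 days), 20% to 40% dissatisfied with comfort, 10% starting on 13 mm. For a comfort-pain correlation of 0 / 0.3 / 0.5 / 0.7, false rejection is 5% / 17-20% / 39-49% / 63-77%. From 0.3 upward it almost always shows fewer pain days on 13 mm.

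**The case against.** **The comparator may be named elsewhere.** The redacted opening of 8.4.2 may point to fuller methods. A reader might infer that the plan omits the comparison altogether; the documents do not support that. What stands is that the visible text is open to two readings.

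**Between-size may be the intended reading.** Section 8.4.2 also applies rank-sum to adequate relief summed over the treatment weeks, which fits a comparison of groups, and the next sentence names 10 mm versus 13 mm. That reading is at least as natural as baseline versus treatment. It removes the pairing problem and leaves the selection on comfort.

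**A paired test need not gain power for pain.** Section 5.2 excludes anal or rectal pain in the past month, so baseline pain is likely sparse. For such items rank-sum matches or beats signed-rank at correlations of 0.3 to 0.5. It would be wrong to infer that the planned test generally hides harm: the reliable gain is a correct error rate. New bleeding or moderate to severe diary pain also triggers anoscopy (7.1, 7.3.8), whatever this p-value shows.

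**The selection should not be overstated.** Subjects who start on 13 mm stay there whatever their comfort, and uncomfortable weak responders stay on 10 mm. Switching near 90% would clash with 20% to 40% discomfort, which caps it at 60% to 80%. Nor does 8.4.2 contradict itself about the fitting data, since it says openly that they determine size. They still shape the groups that are compared.

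**Little rests on these tests.** The primary and secondary hypotheses in 8.1 are versus baseline, and the size ANCOVA is to be done only where appropriate. This limits the severity and does not make the contrast interpretable.

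**Conclusion.** The point holds in two parts. The firmer one is that the main study's 10 mm versus 13 mm ANCOVA compares non-randomised groups formed partly by fitting-period response and comfort, and baseline adjustment does not repair that. The bias runs towards 13 mm looking less effective. The range of about 10% to 65% false rejection rests on the assumed spread of response, switching share and starting share; only the direction is firm.

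The second part is a clarification. On the visible text the diary adverse-event comparison is unnamed. Read as paired, the test is conservative under positive correlation, with a power loss that depends on the item. Read as between sizes, it is confounded by comfort.

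A reader might infer that the primary efficacy result or the sample size is affected. Neither is: the 8.1 analyses are against baseline, and no hypothesis, stated power or sample size uses these tests. Severity is minor to should-fix.

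**What to change.** In 8.4.2:
- Label every main-study 10 mm versus 13 mm contrast, the ANCOVA and any rank-sum comparison, as descriptive, between non-randomised groups selected partly on fitting-period response and comfort. Report the estimate with its interval and draw no conclusion on the relative effect or tolerability of the sizes.
- Name the diary adverse-event comparison, after checking whether the redacted text or another document already does. If it is baseline versus treatment, use the Wilcoxon signed-rank test (McNemar for yes/no items) and report the numbers worse, same and better. If it is 10 mm versus 13 mm, rank-sum can stay under the descriptive label.

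In 8.3, if the paired test is adopted, add a sentence on how the imputation adjustment applies to it.

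The cost is a few sentences, agreed before analysis. The data, patients, visits, fitting rule and 8.1 analyses versus baseline are unchanged.
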